11.5.5.2 Pregnancy

Subjects will be counseled to inform the investigator of any pregnancy that occurs during study treatment and for 90 days after the last dose of study drug.

If a subject, or the female partner of a male subject, becomes pregnant while participating in the study, the study drug will be permanently discontinued immediately. The investigator will 1) notify the medical monitor and Vertex GPS within 24 hours of the site's knowledge of the subject's (or partner's) pregnancy, and 2) send the Pregnancy Information Collection Form to Vertex GPS.

A subject (or their partner, if relevant) who becomes pregnant while on study will be followed until the end of the pregnancy only if on blinded treatment, or if they have been unblinded and have received active drug. The infant will be followed for 1 year after birth, provided informed consent is obtained. A separate ICF will be provided to explain these follow-up activities. Pregnancy itself is not an AE.

12 STATISTICAL AND ANALYTICAL PLANS

This section presents a summary of the planned analyses of safety, efficacy, and clinical pharmacology results. Statistical analysis details on safety and efficacy will be provided in the statistical analysis plan (SAP), clinical pharmacologic analysis details will be provided in the clinical pharmacology analysis plan (CPAP), and population PK-PD analysis details will be provided in the Modeling and Simulation Plan, all of which will be finalized before clinical database lock.

Final analyses will take place after all subjects have completed the study, all data have been entered in the clinical study database, and the database has been locked.

12.1 Sample Size and Power

The primary objective is to evaluate efficacy of VX-561. The primary efficacy endpoint is the absolute change in ppFEV₁ from baseline at Week 12. Based on the initial study design that included 4 dose groups of VX-561 and an IVA 150 mg q12h dose group, assuming a within-group SD of 7 percentage points and a 10% dropout rate at Week 12: a sample size of 22 subjects in the 50, 150, and 250 mg qd VX-561 arms will provide a 95% CI of ± 3.4 percentage points around the observed mean absolute change in ppFEV₁ from baseline at Week 12, based on 2-sided, 1-sample t statistics; a sample size of 11 subjects in the other arms will provide a 95% CI of ± 5.4 percentage points around the observed mean.

Following discontinuation of the 25 mg qd VX-561 and 50 mg qd VX-561 treatment arms, the remaining subjects planned to enroll will be randomized in a 2:2:1 ratio to the 3 current treatment arms with a sample size of approximately 28 subjects for the 250 mg qd VX-561 treatment arm, approximately 28 subjects for the 150 mg qd VX-561 treatment arm, and approximately 14 subjects for the IVA 150 mg q12h treatment arm. The total study sample size including discontinued arms and current arms is approximately maintained as planned (N = 88). Under the same assumption as the original design (within-group SD of 7 percentage points and 10% dropout rate at Week 12): a sample size of 28 subjects in the 250 mg qd VX-561 and 150 mg qd

VX-561 arms will provide a 95% CI of ± 2.9 percentage points around the observed mean absolute change in ppFEV₁ from baseline at Week 12, based on 2-sided, 1-sample t statistics; a sample size of 14 subjects in the IVA 150 mg q12h arm will provide a 95% CI of ± 4.4 percentage points around the observed mean.

12.2 Analysis Sets

The study will include the following analysis sets:

- The All Subjects Set is defined as all subjects who were randomized or received at least 1 dose of study drug. The All Subjects Set will be used for individual subject data listings and disposition summary tables, unless otherwise specified.
- The Full Analysis Set (FAS) will include all randomized subjects who carry the intended CFTR allele mutation and have received at least 1 dose of study drug in the Treatment Period. The FAS will be used for all PD and efficacy analyses in which subjects will be analyzed according to their randomized treatment group, unless otherwise specified.
- The Safety Set will include all subjects who received at least 1 dose of study drug. All safety and study drug exposure will be summarized for the Safety Set.
- The PK Set will include all subjects who received at least 1 dose of study drug and for whom the primary PK data are considered sufficient and interpretable.

12.3 Statistical Analysis

This section summarizes the statistical analysis of safety and efficacy data. The Vertex Biometrics Department or designee will analyze the safety and efficacy data. Methodological and related details will be in the SAP.

12.3.1 General Considerations

The precision standards for reporting safety and efficacy variables are provided in an internal Biometrics document that specifies the programming rules, including the precision for derived variables.

Continuous variables will be summarized using the following descriptive summary statistics: the number of subjects (n), mean, SD, median, minimum value (min), and maximum value (max).

Categorical variables will be summarized using counts and percentages.

Baseline value, unless specified otherwise, will be defined as the most recent non-missing measurement (scheduled or unscheduled) collected before the first dose of study drug. For ECG, baseline will be defined as the most recent pretreatment measurement (or the average of triplicate measurements, if the most recent pretreatment measurement is obtained in triplicate) before the first dose of study drug. Further details on baseline definition will be provided in SAP.

Absolute change from baseline will be calculated as Post-baseline value – Baseline value.

Relative change from baseline will be calculated and expressed in percentage as 100% × (Post-baseline value – Baseline value)/Baseline value.

Treatment-emergent (TE) Period will include the time period starting from the date of the first dose of study drug to 28 days after the last dose date of study drug taken in the treatment period,

or the completion date of study participation, whichever comes earlier. The TE Period will be used for safety analyses unless specified otherwise.

Visit windowing rules: The analysis visit windows for protocol-defined visits will be in the SAP.

12.3.2 Background Characteristics

12.3.2.1 Subject Disposition

The number of subjects in each category (including All Subjects Set, Randomized, FAS, Safety Set) will be summarized overall and by treatment group.

The number and percent (based on the FAS) of subjects in each disposition category (including completed treatment, completed study, and discontinued treatment or study with a breakdown of the reasons for discontinuation) will be summarized overall and by treatment group.

A listing will be provided for subjects who discontinued treatment or who discontinued study with reasons for discontinuation. A randomization listing of subjects will be provided.

12.3.2.2 Demographics and Baseline Characteristics

Demographics, medical history, and baseline characteristics will be summarized overall and by treatment group based on the FAS. No statistical tests will be done to evaluate baseline imbalances between groups.

Demographic and baseline characteristics will include, but are not limited to age (in years), sex, ethnicity, race, weight (kg), height (cm), body mass index (BMI, in kg/m²), baseline ppFEV₁, and baseline sweat chloride.

Medical history will be summarized by MedDRA System Organ Class (SOC) and Preferred Term (PT).

12.3.2.3 Prior and Concomitant Medications

Medications used will be coded using the World Health Organization-Drug Dictionary (WHO-DD) and categorized as the following:

Prior medication: any medication that started before the date of the first dose of study drug, regardless of when the medication ended.

Concomitant medication: medication continued or newly received on or after the date of the first dose of study drug through the end of the TE Period.

Post-treatment medication: medication continued or newly received after the TE Period.

A given medication may be classified as a prior, concomitant medication, or post-treatment medication; both prior and concomitant; both concomitant and post-treatment; or prior, concomitant, and post-treatment. If a medication has a missing or partially missing start/end date or time and if it cannot be determined whether it was taken before the first dose of study drug, concomitantly during the TE Period, or after the TE Period, it will be considered in all 3 categories of prior, concomitant, and post-treatment medication.

Prior medications and concomitant medications will be summarized descriptively using frequency tables by Preferred Name based on the FAS. Post-treatment medications will be provided separately in an individual subject data listing.

Details for imputing missing or partial start and/or stop dates of medication will be in the SAP.

12.3.2.4 Study Drug Exposure and Compliance

Study drug exposure will be summarized overall and by treatment, based on the Safety Set in terms of duration of treatment a subject received (in days), defined as: last dose date – first dose date + 1 day, regardless of study drug interruption.

Study drug compliance will be summarized overall and by treatment group based on the FAS, and will be calculated as: $100 \times [1 - (\text{total number of days of study drug interruption}) / (\text{duration of study drug exposure in days})]$.

In addition, percentage of tablets taken will also be summarized overall and by treatment group based on the FAS, and will be calculated as: $100 \times [(\text{total number of tablets dispensed}) - (\text{total number of tablets returned}) / (\text{total number of tablets planned to be taken per day} \times \text{duration of study drug exposure in days})]$.

12.3.3 Efficacy and Pharmacodynamic Analyses

All efficacy and PD analyses described in this section will be based on the FAS, unless specified otherwise.

12.3.3.1 Efficacy: Spirometry

The efficacy data from the discontinued arms (25 mg qd VX-561 and 50 mg qd VX-561) will not be included in the model and will be summarized descriptively.

The primary efficacy endpoint is the absolute change in ppFEV₁ from baseline at Week 12. The primary analysis (described below) is based on the within group mean of absolute change from baseline for 250 mg qd VX-561, 150 mg qd VX-561, and IVA 150 mg q12h treatment arms.

The primary analysis will be based on a mixed effects model for repeated measures (MMRM) using restricted maximum likelihood. The model will include the absolute change from baseline in ppFEV₁ at Day 15, Week 4, Week 8, and Week 12 from the current treatment arms (250 mg qd VX-561, 150 mg qd VX-561, and IVA 150 mg q12h) as the dependent variable; treatment group, visit, and treatment by visit as fixed effects; with continuous baseline ppFEV₁ as covariates; and an unstructured covariance structure for the within-subject errors. If the model estimation does not converge, a compound symmetry covariance structure will be used.

The primary results obtained from the model will be the within-group treatment effect estimate at Week 12 for each treatment arm. The adjusted mean with a 2-sided 95% CI will be presented in a table.

In addition, the adjusted mean and 95% CI of the treatment effect difference between each VX-561 arm and the IVA arm obtained from the MMRM model will be provided.

12.3.3.2 Pharmacodynamics: Sweat Chloride

The secondary endpoint is the absolute change from baseline in sweat chloride at Week 12 and will be analyzed similarly to ppFEV₁ for 250 mg qd VX-561, 150 mg qd VX-561, and IVA 150 mg q12h treatment arms. Adjusted means and 95% CIs of the average treatment effects at Week 12 will be obtained for within-group (for each arm) and between-group comparisons (between each VX-561 arm and the IVA arm). Details will be provided in the SAP.

12.3.4 Safety Analysis

The overall safety profile of study drug will be assessed in terms of the following safety and tolerability endpoints:

- AEs
- Clinical laboratory values (hematology, serum chemistry, coagulation studies, and urinalysis)
- Standard 12-lead ECGs
- Vital signs
- Pulse oximetry

Safety endpoints will be analyzed based on the Safety Set (including the 25 mg qd VX-561 and 50 mg qd VX-561 treatment arms that were discontinued). Only a descriptive analysis of safety will be performed.

All safety data from the TE period will be summarized by treatment group and overall. All safety data will be presented in individual subject data listings.

12.3.4.1 Adverse Events

AEs will be classified as pretreatment AEs, treatment-emergent adverse events (TEAEs), or post-treatment AEs defined as follows:

Pretreatment AE: any AE that started before the first dose date of study drug.

TEAE: any AE that worsened (either in severity or seriousness) or that was newly developed on or after the first dose date of study drug through the end of the TE Period.

Post-treatment AE: any AE that worsened or that was newly developed beyond the TE Period.

For AEs with completely missing or partially missing start dates, if there is no clear evidence that the AEs started before or after study treatment, the AEs will be classified as TEAEs.

Details for imputing missing or partial start dates of AEs are in the SAP.

AE summary tables will be presented for TEAEs only, overall and by treatment group, and will include the following:

- All TEAEs
- TEAEs by strongest relationship
- TEAEs by maximum severity
- TEAEs leading to treatment discontinuation
- Serious TEAEs
- TEAEs leading to death

Summaries will be presented by MedDRA SOC and PT using frequency counts and percentages (i.e., number and percentage of subjects with an event). When summarizing the number and percentage of subjects with an event, subjects with multiple occurrences of the same AE or a continuing AE will be counted once. Only the maximum severity level will be presented in the severity summaries, and the strongest relationship level will be presented in the relationship summaries.

In addition, a listing of individual subject AE data for TEAEs leading to treatment discontinuation, SAEs, and deaths will be provided separately. All AEs, including pretreatment AEs, will be in an individual subject data listing.

12.3.4.2 Clinical Laboratory Assessments

For treatment-emergent laboratory measurements, the raw values and change from baseline values of the continuous hematology and chemistry results, including coagulation results will be summarized in SI units by treatment group and visit.

The number and percentage of subjects meeting a threshold analysis criterion during the TE Period will be summarized overall and by treatment group. The threshold analysis criterion shift from baseline will also be summarized for selected laboratory parameters. The threshold criteria will be provided in the SAP.

Results of urinalysis and the urine/serum pregnancy test will be in individual subject data listings only.

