8.2 Exclusion Criteria

1. History of any comorbidity that, in the opinion of the investigator, might confound the results of the study or pose an additional risk in administering study drug to the subject.
2. History of clinically significant cirrhosis with or without portal hypertension.
3. Any of the following abnormal laboratory values at screening:
 - Hemoglobin < 10 g/dL
 - Total bilirubin $\geq 2 \times$ upper limit of normal (ULN)
 - Aspartate transaminase (AST), alanine transaminase (ALT), gamma-glutamyl transferase (GGT), or alkaline phosphatase (ALP) $\geq 3 \times$ ULN
 - Abnormal renal function defined as glomerular filtration rate ≤ 50 mL/min/1.73 m² (calculated by the Modification of Diet in Renal Disease Study Equation)^{10,11} for subjects ≥ 18 years of age
4. An acute upper or lower respiratory infection, pulmonary exacerbation, or changes in therapy (including antibiotics) for sinopulmonary disease within 28 days before the first dose of study drug.
5. Lung infection with organisms associated with a more rapid decline in pulmonary status (e.g., *Burkholderia cenocepacia*, *Burkholderia dolosa*, and *Mycobacterium abscessus*). For

subjects who have had a history of a positive culture, the investigator will apply the following criteria to establish whether the subject is free of infection with such organisms:

- The subject has not had a respiratory tract culture positive for these organisms within the 12 months before the date of informed consent.
 - The subject has had at least 2 respiratory tract cultures negative for such organisms within the 12 months before the date of informed consent, with the first and last of these separated by at least 3 months, and the most recent 1 within the 6 months before the date of informed consent.
6. An acute illness not related to CF (e.g., gastroenteritis) within 14 days before the first dose of study drug.
 7. Standard 12-lead ECG demonstrating QTcF >450 msec at screening. If QTcF exceeds 450 msec, the ECG will be repeated 2 more times, and the average of the 3 QTcF values will be used to determine the subject's eligibility.
 8. History of solid organ or hematological transplantation.
 9. History of alcohol or drug abuse in the past year, including, but not limited to, cannabis, cocaine, and opiates, as deemed by the investigator.
 10. Ongoing or prior participation in a study of an investigational treatment with the exception of the following:

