8.4.2 Clinical Laboratory

For the treatment-emergent laboratory assessments, the observed values and change from baseline values of the continuous hematology, chemistry, and coagulation results will be summarized in SI units at each scheduled visit by treatment groups.

The number and percentage of subjects with continuous hematology, chemistry and coagulation test values meeting at least 1 threshold analysis criterion event, during the TE period, will be summarized by treatment groups. The threshold analysis criteria are provided in [Appendix E](#).

Results of urinalysis and positive urine/serum pregnancy tests will be listed in individual subject data listings only. For positive serum pregnancy listing, subjects with serum HCG which are abnormally high will be selected.

In addition, a listing containing individual subject hematology, chemistry, and coagulation values will be provided. This listing will include data from both scheduled and unscheduled visits.

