Appendix E: Criteria for Threshold Analysis

Table 11-3 Threshold Analysis Criteria for Laboratory Tests (as applicable)

Parameter	Threshold Analysis	Comments
Clinical Chemistry (LFT)		
ALT	>ULN - ≤3xULN >3x - ≤ 5xULN >5x - ≤ 8xULN >8x - ≤ 20.0xULN >20.0xULN	FDA DILI Guidance Jul 2009.
AST	>ULN - ≤3xULN >3x - ≤ 5xULN >5x - ≤ 8xULN >8x - ≤ 20.0xULN >20.0xULN	FDA DILI Guidance Jul 2009.
ALT or AST	(ALT>ULN - ≤ 3xULN) or (AST>ULN - ≤ 3xULN) (ALT>3x - ≤ 5xULN) or (AST>3x - ≤ 5xULN) (ALT>5x - ≤ 8xULN) or (AST>5x - ≤ 8xULN) (ALT>8x - ≤ 20xULN) or (AST>8x - ≤ 20xULN) ALT>20xULN or AST> 20 xULN	FDA DILI Guidance
Alkaline Phosphatase	>ULN - ≤ 1.5xULN >1.5 - ≤ 2.5 xULN >2.5 - ≤ 5.0 x ULN >5.0 - ≤ 20.0 x ULN >20.0 x ULN	FDA DILI Guidance Jul 2009.
Total Bilirubin	>ULN - ≤ 1.5xULN >1.5 - ≤ 2xULN >2 - ≤ 3xULN >3 - ≤ 10xULN >10xULN	FDA DILI Guidance Jul 2009.
Direct Bilirubin	>ULN - ≤ 1.5xULN >1.5 - ≤ 2xULN >2 - ≤ 3xULN >3 - ≤ 10xULN >10xULN	FDA DILI Guidance Jul 2009.
ALT and Total Bilirubin	ALT>3xULN and TBILI>2xULN	FDA DILI Guidance Jul 2009.
AST and Total Bilirubin	AST>3xULN and TBILI>2xULN	FDA DILI Guidance Jul 2009.
(ALT or AST) and Total Bilirubin	(ALT>3xULN or AST>3xULN) and TBILI>2xULN	FDA DILI Guidance Jul 2009.

Table 11-3 Threshold Analysis Criteria for Laboratory Tests (as applicable)

Parameter	Threshold Analysis	Comments
GGT	>ULN - ≤ 2.5xULN >2.5 - ≤ 5.0xULN >5.0 - ≤ 20.0xULN >20.0xULN	CTCAE grade 1-4
Clinical Chemistry (NON-LFT)		
Albumin	<LLN - ≥ 30 g/L <30 - ≥ 20 g/L <20 g/L	CTCAE grade 1-3
Amylase	>1x - ≤ 1.5xULN >1.5x - ≤ 2xULN >2x - ≤ 5xULN >5xULN	Criteria based upon CTCAE
Creatinine	>ULN - ≤ 1.5xULN >1.5 - ≤ 3.0xULN >3.0 - ≤ 6.0xULN >6.0xULN	CTCAE grades 1-4
Lipase	>ULN - ≤ 1.5xULN >1.5x - ≤ 2xULN >2x - ≤ 5xULN >5xULN	Criteria based upon CTCAE
Total protein	<LLN >ULN	No CTCAE
CPK	>ULN - ≤ 2.5 x ULN >2.5 - ≤ 5 x ULN >5 - ≤ 10x ULN >10 x ULN	CTCAE grades 1-4
Hematology		
Hemoglobin	Hgb decreased (anemia) <LLN - ≥ 100 g/L <100 - ≥ 80 g/L < 80 g/L Hgb increased >ULN - ≤ 20 g/L above ULN >20 g/L above ULN - ≤ 40 g/L above ULN >40 g/L above ULN	CTCAE grade 1-3 CTCAE grade 1-3
Platelets	Platelet decreased <LLN - ≥ 75.0 x 10e9 /L <75.0 - ≥ 50.0 x 10e9 /L <50.0 - ≥ 25.0 x 10e9 /L <25.0 x 10e9 /L Platelet increased >ULN	CTCAE grade 1-4 No CTCAE available

Table 11-3 Threshold Analysis Criteria for Laboratory Tests (as applicable)

Parameter	Threshold Analysis	Comments
Reticulocytes/Erythrocytes (%)	<LLN >ULN	No CTCAE
Coagulation		

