Activated Partial thromboplastin time (PPT)	>ULN - $\leq 1.5 \times$ ULN >1.5 - $\leq 2.5 \times$ ULN >2.5 x ULN	CTCAE grade 1-3
Prothrombin time (PT) International Normalized Ratio (INR)	>ULN - $\leq 1.5 \times$ ULN >1.5 - $\leq 2.5 \times$ ULN >2.5 x ULN	CTCAE grade 1-3

Table 11-4 Threshold Analysis Criteria for ECGs

Parameter	Threshold Analysis	Comments
HR	Bradycardia	Per HV grade 2, 3, plus shift change
	<50 bpm <45 bpm Decrease from baseline ≥ 10 bpm Decrease from baseline ≥ 20 bpm <50 bpm and decrease from baseline ≥ 10 bpm <50 bpm and decrease from baseline ≥ 20 bpm	
	Tachycardia	Per HV grade 1, 2, 3, plus shift change
	>100 bpm >115 bpm >130 bpm Increase from baseline ≥ 10 bpm Increase from baseline ≥ 20 bpm >100 bpm and increase from baseline ≥ 10 bpm >100 bpm and increase from baseline ≥ 20 bpm	
PR	≥ 240 ms	
	≥ 300 ms ≥ 200 ms and increase from baseline ≥ 40 ms ≥ 200 ms and increase from baseline ≥ 100 ms	
QRS	>110 ms	
	>160 ms Increase from baseline ≥ 20 ms Increase from baseline ≥ 40 ms	
QTc		To be applied to any kind of QT correction formula.
Borderline Prolonged Additional	>450 ms (Male) and <500ms; >470 ms and <500ms (Female) ≥ 500 ms Increase from baseline Increase from baseline >10 ms Increase from baseline >20 ms Increase from baseline >40 ms Increase from baseline >60 ms	

Table 11-5 Threshold Analysis Criteria for Vital Signs

Parameter	Threshold Analysis	Comments
HR	Same as above in ECG category	
SBP increased	>140 mmHg >160 mmHg >10 mmHg increase from baseline >20 mmHg increase from baseline >140 mmHg and >10 mmHg increase from baseline >140 mmHg and >20 mmHg increase from baseline >160 mmHg and >10 mmHg increase from baseline >160 mmHg and >20 mmHg increase from baseline	809/770 analyses
SBP decrease	<90 mmHg <80 mmHg >10 mmHg decrease from baseline >20 mmHg decrease from baseline <90 mmHg and >10 mmHg decrease from baseline <90 mmHg and >20 mmHg decrease from baseline <80 mmHg and >10 mmHg decrease from baseline <80 mmHg and >20 mmHg decrease from baseline	Per HV grade 1, 3, plus shift change

Table 11-5 Threshold Analysis Criteria for Vital Signs

Parameter	Threshold Analysis	Comments
DBP increased	>90 mmHg >100 mmHg >5 mmHg increase from baseline >10 mmHg increase from baseline	
	>90 mmHg and >5 mmHg increase from baseline >90 mmHg and >10 mmHg increase from baseline >100 mmHg and >5 mmHg increase from baseline >100 mmHg and >10 mmHg increase from baseline	

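### SAP 8.4.2 omits the laboratory shift-from-baseline summary planned in Protocol 12.3.4.2, so no planned categorical output separates pre-existing from new or worsened elevations in the lowest bands

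*Protocol*

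**What the plan says.** Protocol 12.3.4.2 plans two categorical laboratory outputs alongside the continuous summaries. The first is a count: "The number and percentage of subjects meeting a threshold analysis criterion during the TE Period will be summarized overall and by treatment group". The second follows directly: "The threshold analysis criterion shift from baseline will also be summarized for selected laboratory parameters". The protocol does not name the parameters, and it leaves the threshold criteria to the SAP.

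SAP 8.4.2 first states that "the observed values and change from baseline values of the continuous hematology, chemistry, and coagulation results will be summarized", at each scheduled visit and by treatment group. It then gives the matching count, of subjects with values "meeting at least 1 threshold analysis criterion event, during the TE period, will be summarized by treatment groups". It ends with listings of individual values. It contains no shift summary, selects no parameters for one, and does not say why. The SAP Introduction states that it is based on Protocol Version 2.0, so this is not a comparison with superseded text.

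The laboratory criteria in SAP Appendix E (Table 11-3) are fixed limits or multiples of ULN. For example, the combined transaminase row starts with "ALT>ULN - ≤ 3xULN) or (AST>ULN - ≤ 3xULN". None refers to the subject's baseline. Elsewhere the SAP does use baseline: the QRS criteria in Table 11-4 include "Increase from baseline ≥ 20 ms", the blood pressure and weight criteria in Table 11-5 include change from baseline, and SAP 8.4.5 keeps a shift summary for pulse oximetry.

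On entry, Protocol 8.1 (criterion 4) requires uninterrupted IVA for at least 28 days before screening. Protocol 8.2 (criterion 3) excludes AST, ALT, GGT or ALP only at 3×ULN or more, and total bilirubin only at 2×ULN or more, at screening.

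**The concern.** The safety question here is what changes when a subject who is stable on IVA moves to VX-561. Take a subject who enters with ALT at 2×ULN and stays there. That subject is counted in the >ULN to ≤3×ULN row for the treatment-emergent (TE) period, alongside a subject whose ALT rose from normal to 2×ULN. The count cannot tell them apart. The planned shift summary would have done so, and the SAP does not carry it over.

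The omission looks unintended. Laboratory data, ECGs, vital signs and pulse oximetry all have categorical safety summaries, and only the laboratory summary has no baseline reference. What is at stake is how the low-band rows are read in a dose-selection study with small arms. No test or error rate is involved, because safety is descriptive only.

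**Working it through.** The plan gives no figure to reproduce. The check is a comparison of the texts, a mapping of the entry limits onto the bands, and an illustration under stated assumptions.

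**Step 1: the two sections side by side.**

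| Output | Protocol 12.3.4.2 | SAP 8.4.2 |
|---|---|---|
| Continuous values and change from baseline | yes | yes |
| Threshold count in the TE period | yes, no baseline condition | yes, no baseline condition |
| Threshold shift from baseline | yes, selected parameters | absent |

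The count is defined in the same way in both documents. Only the shift is lost.

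**Step 2: which Appendix E bands a subject can already occupy at an eligible screening value** (multiples of ULN; limits from Protocol 8.2, bands from SAP Table 11-3).

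| Parameter | Eligible below | Open at entry | Partly open | Closed at entry |
|---|---|---|---|---|
| ALT, AST | 3 | >1 to ≤3 (short of exactly 3) | none | all above 3 |
| ALP | 3 | >1 to ≤1.5; >1.5 to ≤2.5 | >2.5 to ≤5 (values below 3) | above 5 |
| GGT | 3 | >1 to ≤2.5 | >2.5 to ≤5 (values below 3) | above 5 |
| Total bilirubin | 2 | >1 to ≤1.5; >1.5 to ≤2 (short of exactly 2) | none | all above 2 |

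The combined criteria need ALT or AST above 3×ULN with bilirubin above 2×ULN, so they cannot be met at an eligible screening value. The protection is not complete: the limits apply at screening, whereas baseline is the last value before the first dose, and a value may rise in between. Amylase, lipase and CPK have no entry limit, so any of their bands may be occupied at entry.

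**Step 3: illustration of size.** Inputs: n = 28 per current VX-561 arm and n = 14 for IVA (Protocol 12.1). Assumptions not in the documents: a prevalence p of a baseline elevation that persists on treatment, varied from 5% to 30%, and new onset q = 5% among subjects with normal baseline.

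- Expected pre-existing cases = n × p
- Chance of at least one = 1 − (1 − p)^n
- Pre-existing share of the row = p / [p + (1 − p)q]
- Chance of imbalance = the binomial probability that the observed baseline prevalences in arms of 28 and 14 differ by 10 percentage points or more when both have the same p

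At p = 10%: 28 × 0.10 = 2.8; 14 × 0.10 = 1.4; 1 − 0.90^28 = 0.948; share = 0.10 / (0.10 + 0.90 × 0.05) = 0.10 / 0.145 = 0.69.

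| p | Expected, n = 28 | Expected, n = 14 | At least one, n = 28 | Share pre-existing | Imbalance ≥10 points |
|---|---|---|---|---|---|
| 5% | 1.4 | 0.7 | 76.2% | 51.3% | 18.5% |
| 10% | 2.8 | 1.4 | 94.8% | 69.0% | 35.6% |
| 20% | 5.6 | 2.8 | 99.8% | 83.3% | 49.5% |
| 30% | 8.4 | 4.2 | about 100% | 89.6% | 55.3% |

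One subject is 1/28 = 3.6 percentage points in a VX-561 arm and 1/14 = 7.1 in the IVA arm. At the lower sizes in SAP 6.2 these become 1/22 = 4.5 and 1/11 = 9.1. These percentages show how coarse the rows are; they do not measure the effect.

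**The case against.** The case for leaving the SAP alone is substantial. The protocol's own count has no baseline condition and the SAP follows it, so restoring the shift would not alter a single count. The SAP still gives change from baseline by visit, where a subject stable at 2×ULN shows no change, and it lists every value. Stable pre-existing findings are already kept out of the TEAE tables, because a TEAE must be new or worsened, and Protocol 13.1.1.2 ties AE reporting of laboratory findings to clinically significant worsening. Subjects are randomized and all enter on IVA. The protocol promised a shift only for selected, unnamed parameters and left details to the SAP.

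All of this is correct, and it rules out stronger readings that a reader might infer. One is that the omission causes pre-existing elevations to be counted. It does not, since both documents count them. Another is that the SAP keeps only the counts; it also keeps the continuous summaries and the listings. A third is that the VX-561 arms would be made to look worse than IVA. The IVA arm is counted in the same way, so no such bias is expected, only dilution and chance imbalance.

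What remains is the omission. Leaving the choice of parameters to the SAP does not cover a SAP that chooses none and says nothing. Mean change by visit does not show how many subjects moved up a band, the listings would need reconstruction by hand, and AE reporting rests on the investigator's judgement of clinical significance.

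**Conclusion.** The point holds as a narrow one: the SAP leaves out a laboratory output that the protocol plans, without explanation. As written, no planned categorical output separates pre-existing from new or worsened elevations in the ALT/AST band up to 3×ULN, the bilirubin bands up to 2×ULN and the lower ALP and GGT bands.

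A reader might take this as a threat to the detection of serious liver signals. The documents do not support that, because the ALT/AST bands above 3×ULN and the combined transaminase-bilirubin criteria are largely protected by the entry limits. The size is unknown. The figures under the assumed 5% to 30% prevalence and 5% new onset show only what could happen if baseline elevations are that common and persist. The conclusion also rests on SAP 8.4.2 and Table 11-3 being where a shift would appear; both are legible, although other parts of the SAP are redacted. This is a minor correction, worth making because it is nearly free.

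**What to change.** Add to SAP 8.4.2 a table, by treatment group, that crosses baseline band with worst TE-period band using the Appendix E bands, and identify subjects whose worst band is above their baseline band. Name the parameters before data lock and unblinding. ALT, AST, ALP, GGT and total bilirubin are a reasonable selection, given as an example because the protocol leaves the choice open; amylase, lipase and CPK could be added. If the sponsor prefers not to produce the table, the SAP should state and justify the departure from Protocol 12.3.4.2.

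The cost is one table from data already collected and a short addition to the SAP text. The change affects no existing count, visit or sample size.
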